8 RESEARCH QUESTIONS AND OBJECTIVES

The research question to be answered by this study is: *How effective is the VIZAMYL*TM reader training programme in clinical practice in Europe? To answer this question, the study has the following primary and secondary objectives.

Primary:

The primary study objective is to assess the effectiveness of the VIZAMYLTM reader training programmes (in-person or electronic) in Europe by estimating the diagnostic accuracy, sensitivity, specificity, PPV, and NPV, of the visual interpretation of VIZAMYLTM images obtained in the course of clinical practice. Diagnostic accuracy is the overall true-interpretation rate for all subjects. One minus the diagnostic accuracy gives the overall image interpretation error rate.

Secondary:

The secondary study objective is:

Evaluate the impact of demographic and other factors (such as method of training, gap between training and reading, and country) on diagnostic accuracy to try to identify factors that may be associated with image interpretation errors.

Sensitivity is the true-positive (TP) image interpretation rate in subjects with brain amyloid. Specificity is the true-negative (TN) image interpretation rate in subjects without brain amyloid. Positive predictive value (PPV) is the TP image interpretation rate for subjects with positive VIZAMYLTM scans. Negative predictive value (NPV) is the TN image interpretation rate for subjects with negative VIZAMYLTM scans.

9 RESEARCH METHODS

9.1 Study Design

9.1.1 Overall Study Design and Plan

This is a non-interventional PASS with the primary objective of assessing effectiveness of the VIZAMYLTM reader training programmes (in-person or electronic) in Europe by estimating the diagnostic accuracy of the visual interpretation of VIZAMYLTM images by clinical readers recruited from European countries where VIZAMYLTM is commercially available

(each reader will interpret (or will have interpreted) images collected at his/her institution, for a total of at least 200 images). The diagnostic accuracy of image interpretation will be determined across all images as well as for subsets of images by country and by reader. Sensitivity, specificity, PPV, and NPV will also be determined and will be reported as point estimates along with exact 95% CIs. The SOT for classifying each image as correct (TP or TN) or incorrect (false positive or false negative) will be the majority blinded visual interpretations of 5 independent expert readers.

Imaging sites will be selected according to the criteria detailed below in Section 9.2.2. Each imaging site will be assigned a 3-digit identifying number. The VIZAMYLTM images at each participating site will be obtained in clinical practice. Because VIZAMYL is approved and no longer investigational, the need for subject informed consent will be decided at each institution by the local IEC.

All subjects must satisfy all the inclusion criteria and none of the exclusion criteria listed in Section 9.2.3. When required by the local IEC, signed and dated informed consent must be obtained from all subjects or the subject's legally acceptable representative, if applicable, in accordance with local regulations, prior to collection of any study-specific data. Each subject will be assigned a 7-digit identifying number; the first 3 digits will be the identifying number for the site at which the subject's VIZAMYLTM scan was obtained (as described in the preceding paragraph), and the remaining 4 digits will be assigned consecutively at each site. Demographic data (see Table 5) will be recorded for each subject.

The images will be de-identified (i.e., subject identifying information will be removed) so that inspection of an image will not reveal the identity of the subject from whom the image was obtained.

If anatomic images are used in the interpretation of the VIZAMYLTM images, they will also be de-identified and transmitted to the core image lab, and will be interpreted with the VIZAMYLTM images by the expert readers.

The clinical reader eligibility criteria are discussed below in Section 9.2.4. Demographic data (see Table 5) will be recorded for each clinical reader. Each clinical reader will be assigned an identifying letter that starts with C (for Clinical): *CA*, *CB*, *CC*, etc.

During the image interpretations, the clinical readers will not be (or were not) blinded to the subjects' clinical information, but will be blinded to the interpretations of the expert readers

(which will not be available yet). Each clinical reader will interpret the VIZAMYLTM images as they are collected at his/her site. VIZAMYLTM images will be interpreted as positive (significant levels of amyloid present) or negative (significant levels of amyloid absent) according to local practices at the institution; these classifications are consistent with the VIZAMYLTM reader training programme, the VIZAMYLTM Summary of Product Characteristics, and the EANM guidelines on interpretation of amyloid PET images [Minoshima et al. 2016]. If anatomic images (MRI and/or computed tomography [CT]) are available for a subject, the normal institutional clinical practice regarding use of these images in PET interpretation will be followed. The clinical reader will enter his/her interpretation and other data into an eCRF. The site will remove identifying information (except for subject number) from the image and transmit the image electronically to the GE Healthcare image core lab.

The image core lab will assign a randomization code to the image and will remove the subject number.

The \geq 200 images collected in this study will be interpreted separately by each of 5 expert readers, who will classify each image as positive or negative for brain amyloid. The expert readers will consist of 5 experienced nuclear medicine physicians or radiologists, with extensive experience in PET imaging (including amyloid imaging), who have completed a VIZAMYLTM training programme. The selection criteria for these 5 expert readers are detailed below in Section 9.2.6. The expert readers will be blinded to the subjects' clinical information and to the interpretations of the other expert readers and clinical readers, and will not be permitted to discuss images or interpretations with anyone. The expert read will result in at least $200 \times 5 = 1000$ expert blinded visual interpretations, which will be analysed by subject to determine the majority blinded visual interpretation, as follows. Each image will have 5 expert interpretations, each of which will be positive or negative. The image interpretation (positive or negative) made by the majority of the 5 expert readers will be taken as the majority interpretation. For example, if 3, 4, or 5 of the expert readers interpreted a specific subject's image as positive, then the majority interpretation for that image will be positive. The result of this analysis will be at least 200 majority interpretations (1 per image). The level of reader certainty will also be recorded on a scale of 1 to 5 (1 = lowest, 5 = highest).

Using subject number, each of the \geq 200 clinical image interpretations will be matched to the corresponding expert reader majority interpretation for the subject and the image interpretation will be classified as a TP, TN, FP or FN using the expert reader majority interpretation as the SOT. For example, if an image interpretation is "positive" and the expert reader majority interpretation is "positive", the image interpretation would be classified a TP. If the expert reader majority interpretation were "negative", however, then the image interpretation would be classified as a FP. The numbers of TP, TN, FP, and FN images among the \geq 200 original images will be used to calculate diagnostic accuracy:

Diagnostic accuracy =
$$(nTP + nTN) / (nTP + nTN + nFP + nFN)$$

Where nTP is the number of true-positive scans, nTN is the number of true-negative scans, nFP is the number of false-positive scans, and nFN is the number of false-negative scans.

Sensitivity, specificity, PPV, and NPV will also be calculated:

Sensitivity =
$$nTP / (nTP + nFN)$$

Specificity = $nTN / (nTN + nFP)$
 $PPV = nTP / (nTP + nFP)$
 $NPV = nTN / (nTN + nFN)$

Treatment-emergent adverse events (AEs) with onset or worsening between the start of VIZAMYLTM injection and subject discharge from the imaging suite will be recorded on an AE eCRF, along with the centre's assessment of relationship to VIZAMYLTM, severity, seriousness, timing, need for treatment, and outcome.

Study procedures for prospective data collection are summarised in the Study Schedule of Events for Prospective Data Collection (Table 2). For collection of existing data, the activities in the "Subject Enrolment" and "Imaging Visit" columns in Table 2 will have occurred in the past and may be obtained from the medical record, including whether or not the patient meets the inclusion and exclusion criteria.

 Table 2
 Study Schedule of Events for Prospective Data Collection

| Procedures | Subject Enrolment | Imaging Visit | Post- Imaging | Responsible |
|--|----------------------|------------------|------------------|-------------|
| Selection of imaging sites | | | | Sponsor |
| Informed consent obtained from subject (if IEC requires) | X | | | Centre |
| Subject inclusion/exclusion criteria assessed | X | | | Centre |
| Subject demographic information recorded | X | | | Centre |
| VIZAMYL™ administration and PET imaging; AE monitoring from start of injection until discharge from imaging centre | | X | | Centre |
| Completion of electronic case report form | | | X | |
| De-identification of subject's images | | | X | Centre |
| Transmittal of subject's images to Sponsor image core lab | | | X | Centre |
| Preparation of images for expert readers | | | X | Sponsor |

The image evaluation by expert readers will be prospective; these activities are summarised in Table 3.

Table 3 Study Schedule of Events for Image Evaluation by Expert Readers

| Procedures | Expert Selection | Expert Image Evaluation | Responsible |
|---|---------------------|-------------------------------|-------------|
| Identification of expert reader candidates | X | | Sponsor |
| Informed consent obtained from expert reader candidates | X | | Sponsor |
| Expert reader candidate inclusion/exclusion criteria assessed | X | | Sponsor |
| Selection of 5 expert readers | X | | Sponsor |
| Expert reader demographic information recorded | X | | Sponsor |
| Independent review of images | | X | Readers |

The criteria for blinding are shown below in Table 4.

Table 4 Blinding of Persons Involved in the Study

| Personnel | Blinded To: |
|-------------------------------|---|
| Subjects | Expert readers' image interpretations |
| Imaging Centre Site Personnel | Expert readers' image interpretations |
| Clinical Readers | Other clinical readers' image interpretations |
| | Expert readers' image interpretations |
| Expert Readers | Clinical readers' image interpretations |
| | Other expert readers' image interpretations |
| | Subject clinical information |

No direct benefits to subjects enrolled in this study are expected. Each subject will be referred for a VIZAMYLTM scan according to clinical need determined by his/her physician. The potential risks to subjects are described in the VIZAMYLTM Summary of Product Characteristics, and include adverse drug reactions and image interpretation errors.

9.2 Setting

This study will allow patients and clinical readers from any healthcare setting (i.e., primary, secondary, and tertiary care) to participate. However, it is anticipated that referrals for VIZAMYLTM imaging will be made predominantly by specialists (e.g., neurologists and psychiatrists) rather than by primary care physicians and that a substantial proportion will be made by dementia specialists who may be based in tertiary care centres. It is anticipated that the main use of amyloid PET imaging will be to assist in the diagnosis of cases of dementia that are difficult because of atypical symptoms and/or early onset), as suggested by the European Federation of the Neurological Societies (EFNS) task force's publication on the use of neuroimaging in the diagnosis of dementia [Filippi et al. 2012]. The type of medical practice for the referring physicians and for the readers will be collected as part of the demographic data.

GE Confidential Page 21 of 43

9.2.1 Selection and Replacement of Countries

The study will be conducted in European countries where VIZAMYLTM is commercially available.

9.2.2 Selection and Replacement of Imaging Sites

Because of the short radioactive half-life (~110 minutes) of the fluorine 18 isotope in [\frac{18}{F}] flutemetamol (the active component of VIZAMYL\text{TM}), the ability to supply VIZAMYL\text{TM} is limited to within a finite radius around each manufacturing site, and therefore only imaging sites that fall within the regions of VIZAMYL\text{TM} supply may participate.

Imaging sites must also meet the instrumentation requirements for PET imaging, obtain Independent Ethics Committee (IEC) approval of the study protocol, have a reasonable probability of conducting amyloid PET imaging (i.e., they must serve the relevant population), agree to obtain written informed consent from potential study subjects when required by the IEC, and agree to collect and transmit subjects' study data.

9.2.3 Selection and Replacement of Subjects

Subjects who receive VIZAMYLTM as part of routine clinical practice will be eligible; patients scheduled for a VIZAMYLTM scan as part of a clinical study will be excluded from this study. When required by the local IEC, subjects must provide written informed consent before any study-specific data are collected. A subject will be considered enrolled in the study if he/she has provided written informed consent (if required) and any study-specific data have been collected about the subject. Subjects meeting the following criteria may be enrolled:

- 1. The subject is an adult (aged 18 years or older) of any race or gender and has been referred for a VIZAMYLTM PET brain scan as part of the assessment of his/her cognitive impairment.
- 2. The VIZAMYL™ scan was ordered as part of the clinical care of the subject and is not exclusively for a clinical trial.
- 3. If informed consent is required by the local IEC, the subject, or his/her legally authorised representative, is willing and able to sign consent for use of their de-identified VIZAMYLTM PET images and associated anatomic images (brain CT and/or MRI) used in the interpretation of the VIZAMYLTM images as well as de-identified demographic information.

Subjects must be excluded from this study if the following criterion is met:

1. If informed consent is required by the local IEC, the subject (or representative) is not willing to consent to their de-identified images and other data being used in this study.

No withdrawal criteria for this study have been formalised. In accordance with the Declaration of Helsinki, each consenting subject is free to withdraw from the study at any time. Subjects who withdraw from the study will be asked if their de-identified data may be used; if consent

to use their de-identified data is withdrawn, every effort will be made to exclude their data from analysis. Incomplete data sets from withdrawn subjects may be excluded from analysis even if permission has been granted for use if critical data are missing. Subjects whose data are excluded from analysis may be replaced.

No termination criteria for this study have been formalised. The Sponsor reserves the right to terminate the study at any time.

[figure not shown]
9.2.4 Inclusion and Exclusion of VIZAMYLTM Images

To be included in efficacy analyses, a subject's VIZAMYLTM PET scan must be interpretable and it must be transferred to the Sponsor.

Interpretability of the image will be determined by the nuclear medicine personnel obtaining the PET scan at each imaging centre. For example, if the subject moves during the scan, the scan may be severely blurred and therefore uninterpretable. Images that are not interpretable will be excluded from efficacy analyses and the subject data will be included in safety analyses only. Additional images may be collected to ensure a minimum of interpretable 200 images.

Images that cannot be transferred to the Sponsor for technical reasons will not be included in analyses and subject data will be included in safety analyses only. Additional images may be collected, if necessary, to ensure a minimum of 200 images total for the efficacy analyses.

9.2.5 Selection and Replacement of Clinical Readers

Each potential clinical reader contacted will be asked to complete a screening survey, which asks, among other things, if they are willing to participate in the study, and if they are authorised by their institution to read VIZAMYLTM PET images. Those who meet eligibility criteria and are willing to participate will be included in the study, 1 to 5 clinical readers per country.

To avoid overrepresentation of any reader, institution, or country in the study results, the following restrictions will apply:

- No clinical reader may contribute more than 7.5% of the total number of images (e.g., 15 of 200 images)
- No institution may contribute more than 15% of the total number of images (e.g., 30 of 200 images)
- No country may contribute more than 25% of the total number of images (e.g., 50 of 200 images)

Page 23 of 43

Additional clinical readers may be added as necessary to replace clinical readers who withdraw. In the event that a clinical reader withdraws, the reason for withdrawal will be recorded, and permission to use his/her data will be sought; if declined, he/she will be replaced and his/her data will not be used.

GE-067-027 C

Version 7.0 Approved

9.2.6 **Selection and Replacement of Expert Readers**

The expert readers will consist of 5 experienced nuclear medicine physicians or radiologists, with extensive experience in PET imaging (including VIZAMYLTM imaging), who have completed the VIZAMYLTM training programme. They may have participated in VIZAMYLTM clinical trials. The expert readers will have a minimum of 5 years of experience in nuclear medicine brain imaging and must have reviewed a minimum of 100 amyloid PET images within the previous 5 years from the start of the study.

In the event that an expert reader withdraws, the reason for withdrawal will be recorded. If the expert reader withdraws before reading all of the images, or withdraws permission to use his/her demographic information, he/she will be replaced. The replacement reader will be asked to read all images and his/her results will be used. The incomplete results from the expert reader who withdrew will not be used.

9.3 Variables

9.3.1 **Demographic Data**

The demographic data listed in Table 5 will be collected about subjects and readers. In addition, every effort will be made to collect these data from readers who decline to participate as well.

Table 5 **Demographic Data to Be Collected**

| Group | Demographic Factors | | |
|------------------|---|--|--|
| Subjects | • Age | | |
| | • Gender | | |
| | • Race | | |
| | Reason for scan | | |
| | • Country | | |
| | Imaging centre | | |
| | Type of medical practice of referring physician (primary, secondary, tertiary) | | |
| | VIZAMYL™ dose in MBq or mCi | | |
| | Type of anatomic images available, if any (MRI and/or CT) | | |
| Clinical readers | • Age | | |
| | • Gender | | |
| | • Race | | |
| | • Country | | |
| | • Institution | | |
| | VIZAMYL TM reading training status | | |
| | • VIZAMYL TM reading training method (electronic, in-person, or both) | | |
| | • Date(s) of VIZAMYL TM reading training (this will be used to determine the time from | | |
| | last training to the date of image interpretation) | | |
| | Training with other amyloid PET imaging agents | | |

[figure not shown]

Table 5 Demographic Data to Be Collected

| Group | Demographic Factors |
|-------|---|
| | Medical specialty |
| | Years of experience reading PET images |
| | Number of brain PET scans read in clinical practice |
| | Type of medical practice (primary, secondary, tertiary) |
| | • Prior experience (clinical or research) with any amyloid PET imaging agent (including |
| | VIZAMYL TM) |

9.3.2 Exposures

Subjects will receive (or will have received) VIZAMYLTM intravenously prior to PET imaging, according to clinical practice.

Clinical readers may or may not have completed any training in reading VIZAMYLTM images, and some may have completed 1 or more VIZAMYLTM reader training programmes. They also may or may not have prior experience in reading VIZAMYLTM images.

Expert readers will have been trained in reading VIZAMYLTM images and will have experience in reading amyloid PET images.

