9.3.3 Outcome Measures

The primary outcome measure will be diagnostic accuracy (point estimates and exact 95% CIs) determined across all images (at least 200 images), as indicators of the collective proficiency of the clinical readers at interpreting VIZAMYLTM PET images. Diagnostic accuracy will give an indication of the overall image interpretation error rate (1 minus diagnostic accuracy). Additional outcome measures will be sensitivity, specificity, PPV, and NPV.

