9.5 Study Size

Number of Subjects

This study has no formal hypothesis and no statistical tests will be performed. The endpoints of accuracy, sensitivity, and specificity will be summarised descriptively with point estimates and

95% CIs. Although no formal hypothesis will be tested, the sample size is determined to achieve the desired precision in estimating the primary endpoint of the percentage of subjects whose images are correctly classified as positive or negative (accuracy). Assuming that VIZAMYLTM images from 90% of subjects are read correctly by readers who have taken the VIZAMYLTM training programme, 200 subjects will achieve a 95% CI width of less than 10%.

The endpoints of sensitivity and specificity will also be summarised descriptively. This study aims to characterise reader performance in clinical practice so the number of positive and negative images will not be controlled. However, it is expected that most patients who are referred for a VIZAMYLTM scan will have dementia, and most cases of dementia are AD. Since brain amyloid is present in AD, it is expected that the majority of patients in this study will have brain amyloid. It is assumed that the majority blinded interpretation of the expert readers will be SOT-positive for approximately 65% of scans, giving a total of approximately 130 scans for sensitivity, with the remaining 70 scans being SOT-negative and therefore usable for calculating specificity. Assuming a sensitivity of 90% and a specificity of 90%, these sample sizes should give reasonably precise 95% CIs for estimating sensitivity and specificity in this scenario (95% CI width of approximately 15% or less).

Accuracy, sensitivity, and specificity will also be calculated by country where all study images from sites within a given country will be pooled for analysis. No country may contribute more than 25% of the total number of images. Because the number of subjects per country is smaller than the overall number of subjects, the level of precision and the width of the CI will be impacted. Again, since the aim of the study is to characterise reader performance in clinical practice, the exact number of images obtained per country and per site is unknown. Table 6 provides examples of 95% CI widths for accuracy assuming a few different sample sizes per country to illustrate the change in precision.

Table 6 95% Confidence Interval Width for Different Sample Sizes Assuming 90% Diagnostic Accuracy

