The efficacy clinical reader population will consist of each clinical reader who has interpreted the images included from his/her institution and has had their image interpretations classified as TP, TN, FP, or FN through comparison with the SOT (the expert reader majority interpretation).

Page 29 of 43

Subject Demographics/Other Baseline Characteristics

A table will be provided with the following information:

- Number of subjects enrolled.
- Number of subjects in the safety population.
- Number of subjects with VIZAMYLTM images included in the efficacy analysis.

GE-067-027 C

Version 7.0 Approved

Demographic information (Table 5 above) will be summarised using descriptive statistics.

Study Treatments

All subjects will have received VIZAMYLTM as part of routine clinical practice. The dose and volume administered will be summarised across all subjects.

Clinical Reader Demographics/Other Baseline Characteristics

A table will be provided with the following information:

- Number of clinical readers participating.
- Number of clinical readers' image interpretations included in the efficacy analysis.

Demographic information (Table 5 above) will be summarised using descriptive statistics. Demographic information will be reported for readers who are randomly chosen to participate as well as the complete pool of potential readers who agreed to participate in addition to readers who decided not to participate where data are available.

Primary Analysis

The primary analysis will be the determination of diagnostic accuracy, sensitivity, specificity, PPV, and NPV across readers based on all evaluable images (at least 200 images) (point estimates and exact 95% CIs).

Secondary Analyses

The numbers and percentages of images for which 5 expert readers agree, 4 expert readers agree, and 3 expert readers agree will be summarised. In addition, results will be analysed by the following variables:

- Country
- Time from training to image interpretation (<6 months, >6 months)
- Specialty of the reader
- Training method(s) used by the clinical reader (in-person, electronic, or both)

- Number of scans read by the clinical reader in practice prior to the study (<50, >50)
- Reader classification certainty (1 to 5)

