2 STUDY OBJECTIVES

2.1 Primary objective

The primary study objective is to assess the effectiveness of the VIZAMYL™ reader training programmes (in-person or electronic) in Europe by estimating the diagnostic accuracy, sensitivity, specificity, positive predictive value (PPV), and negative predictive value (NPV), of the visual interpretation of VIZAMYL™ images obtained in the course of clinical practice. Diagnostic accuracy is the overall true-interpretation rate for all subjects. One minus the diagnostic accuracy gives the overall image interpretation error rate.

At least 200 VIZAMYL™ images obtained in clinical practice will be reviewed (or will have been reviewed) by clinical readers recruited from European countries where VIZAMYL™ is commercially available [REDACTED]

[REDACTED]. The standard of truth (SOT) will be the majority blinded visual image interpretations of the same images by 5 independent expert readers.

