4 STUDY ENDPOINTS

4.1 Primary endpoints

The primary endpoints are the diagnostic accuracy, sensitivity, specificity, PPV, and NPV across readers based on all evaluable images.

Using subject number, each of the ≥ 200 clinical image interpretations will be matched to the corresponding expert reader majority interpretation for the subject and the image interpretation will be classified as a TP, TN, FP or FN using the expert reader majority interpretation as the SOT.

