8.4.2 Clinical Reader - demographic and baseline characteristics

Continuous demographic variable clinical reader's age will be summarised descriptively, and the following categorical demographic and baseline variables will be summarised using counts and percentages. Summaries will be based on the efficacy clinical reader population.

- Gender
- Race
- Country

Baseline characteristics:

- VIZAMYL™ reading training status
- Number of times training done (1, 2, ≥ 3)
- VIZAMYL™ reading training method (electronic, in-person, or both)
- Training with other amyloid PET imaging agents
- Medical specialty
- Time (month) from last training to the date of image interpretation (<6 months, ≥ 6 months)
- Number of brain PET scans read in clinical practice (<50, ≥ 50)
- Type of medical practice (primary, secondary, tertiary)
- Prior experience (clinical or research) with any amyloid PET imaging agent (including VIZAMYL™)

In addition, the following continuous baseline characteristics will be summarised descriptively:

- Duration (months) from last training to the date of image interpretation
- Years of experience reading PET images
- Number of brain PET scans read in clinical practice
- Years of experience reading PET images

- Number of times training done

Listings will be provided for each clinical reader's demographic and baseline characteristics.

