8.6.3 Secondary analysis

Images for which 5 expert readers agree, 4 expert readers agree, and 3 expert readers agree will be summarised using counts and percentages.

In addition, estimates of diagnostic accuracy, sensitivity, specificity, PPV, and NPV, along with exact 95% CIs, will be provided separately for prospective images, retrospective images, and pooled results, separately, using the following variables:

- Country
- Time from training to image interpretation (<6 months, \geq 6 months)
- Specialty of the reader
 - Nuclear Medicine
 - Radiology
 - Medical Physics
 - Other
- Training method (s) used by the clinical reader (in-person, electronic, or both)
- Number of scans read by the clinical reader in practice prior to the study (<50, \geq 50)
- Clinical reader and SOT classification certainty (1 to 5)

The number of clinical readers in the above subgroups will be provided. The number and percentage of diagnostic accuracy categories <70%, >70% to \leq 80%, >80% to \leq 90%, and >90% will also be provided by using the above subgroups for prospective images, retrospective images, and pooled results, separately.

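### The only overall accuracy estimate pools trained and untrained readers, and the plan has no prespecified estimate or subgroup level that separates reads made without prior training (minor)

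*Protocol*

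**What the plan says.** **Objective and sizing.** SAP section 2.1, in line with Protocol section 8, sets out to assess the effectiveness of the "reader training programmes (in-person or electronic) in Europe by estimating the diagnostic accuracy" and related measures. Protocol section 9.5 and SAP section 5 justify 200 subjects by assuming that 90% of images are "read correctly by readers who have taken the" training, which gives a 95% interval narrower than 10 points.

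**Who reads.** Protocol section 9.3.2, repeated in SAP section 3.3, says "Clinical readers may or may not have completed any training in reading" VIZAMYL images. Protocol section 9.2.5 asks readers about willingness and institutional authorisation; the visible text sets no training requirement. Protocol section 4 (Study design) and section 9.4.1 allow existing data, so a clinical read may be older than its reader's training.

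**What is estimated overall.** SAP section 4.1: "The primary endpoints are the diagnostic accuracy, sensitivity, specificity, PPV, and NPV across readers based on all evaluable images". Neither efficacy population has a training criterion. Protocol section 9.3.3 describes the primary result "as indicators of the collective proficiency of the clinical readers at interpreting" VIZAMYL scans.

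**What is broken down.** Protocol section 9.7 lists "Training method(s) used by the clinical reader (in-person, electronic, or both") and time from training, split at 6 months. SAP sections 4.2 and 8.6.3 carry both forward, the method variable again as that "used by the clinical reader (in-person, electronic, or both"). Training status is collected (Protocol Table 5) and tabulated as a reader baseline characteristic (SAP section 8.4.2), but it is not in the accuracy-by-variable lists. SAP section 8.4.2 also defines "Duration (months) from last training to the date of image interpretation". SAP section 7.1, on derived variables, is marked not applicable.

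**The concern.** The research question can be read in two ways: how accurate readers are as they are found in practice, or how accurate they are after training. The plan sizes on the second reading and specifies an overall estimate only for the first. The two coincide when every read followed training, and nothing in the plan guarantees that.

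If some reads were made without prior training, three things follow.

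- The mixed figure would be reported under an objective worded as training effectiveness.
- Reads by never-trained readers fit no level of training method or time from training. Because missing values stay missing (SAP section 7.2), they would probably drop out of those tables while remaining in the primary figure, so the breakdowns and the total would not describe the same reads.
- A read made before the reader's last training has a negative interval. No stated rule keeps it out of the under-6-months level, where it would be shown as a recently trained read. Time since training is one of the factors named in the secondary objective.

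**Working it through.** **1. The plan's own figure.** Inputs: n = 200, accuracy 90% (Protocol section 9.5, SAP section 5), two-sided exact 95% interval (SAP section 8.1). The Clopper-Pearson limits are the 2.5% quantile of Beta(x, n−x+1) and the 97.5% quantile of Beta(x+1, n−x). For x = 180 they are 85.0% and 93.8%, a width of 8.8 points, so the stated width below 10 points reproduces. Protocol Table 6 also reproduces (24.4, 20.9, 18.5 and 16.7 points at n = 30, 40, 50 and 60).

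**2. Shift in the pooled estimate.** The documents give neither the share of untrained reads, u, nor the accuracy of such reads, a; both are assumptions here. Pooled accuracy = (1−u) × 0.90 + u × a. The reader cap in Protocol section 9.2.5 is 7.5%, or 15 of 200 images, so one untrained reader at the cap gives u = 0.075.

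- u = 0: 0.900, no shift.
- a = 0.70: 0.925 × 0.90 + 0.075 × 0.70 = 0.885, a shift of 1.5 points.
- a = 0.80: 0.925 × 0.90 + 0.075 × 0.80 = 0.8925, a shift of 0.75 points.
- a = 0.90: no shift at any u.

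Both shifted values lie inside 85.0% to 93.8%. The expected pooled value reaches the lower limit (84.98%) only at u = (0.90 − 0.8498)/(0.90 − a), which is 25% for a = 0.70 and 50% for a = 0.80.

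**3. Precision of the pooled estimate under mixing.** At 177/200 (88.5%) the width is 9.3 points. At 173/200 the interval is 81.0% to 90.9%, a width of 9.9 points. At 172/200 it is 10.1. The width below 10 points therefore holds for the pooled figure down to 173/200.

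**4. Precision of a trained-only estimate**, at about 90% accuracy and assuming independent reads:

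| Trained reads | Correct | Exact 95% interval | Width (points) |
|---|---|---|---|
| 200 | 180 | 85.0% to 93.8% | 8.8 |
| 185 (one reader at the cap removed) | 166 or 167 | 84.4% to 93.7%, or 85.1% to 94.1% | 9.3 or 9.1 |
| 160 | 144 | 84.3% to 94.2% | 9.9 |
| 140 | 126 | 83.8% to 94.4% | 10.6 |

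At exactly 90% (count not rounded) the width is 9.97 points at 158 reads and 10.01 at 157. The stated precision therefore covers trained readers if at least 158 of 200 reads follow training, that is, if no more than 42/200 = 21% do not.

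**The case against.** The pooled estimate is a deliberate choice. Protocol section 9.3.3 defines the primary outcome as the clinical readers' collective proficiency, and section 7 says the EMA asked for the error rate in clinical practice. An all-reader figure answers that request. This stands, and the estimate should be kept.

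Much of the trained-reader result is already planned. All five measures are given with intervals by method and by time from training, accuracy is tabulated by reader (Protocol section 9.5, SAP section 5), and listings cover reader characteristics and image evaluations (SAP sections 8.4.2 and 8.6.2). A trained-reader total could be rebuilt from these. That is true, but the rule for building it would then be chosen after the data were seen.

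Four stronger readings are tempting, and the documents do not support them.

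- *Training status is never to be analysed.* Protocol section 9.3.4 commits in general terms to analysing reader variables, and training status is one of them. The gap is that the specific lists do not carry it through.
- *Reads made before training will be counted as under 6 months.* Protocol sections 9.6.2 and 9.8.1 provide logic checks that might catch a negative interval. What is missing is an explicit rule.
- *The sample size is wrong.* There is no hypothesis test, 90% is a planning value, and the width target survives considerable dilution of the pooled figure (step 3).
- *The primary result will be materially biased.* Protocol section 7 notes that the product information recommends training first, and section 9.9 expects that untrained readers may be unwilling to take part. The share may be small or nil.

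The table templates are in a separate document (SAP section 1), so a row for no training may exist there. The SAP text does not call for one.

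**Conclusion.** The concern holds as a minor gap in specification. Both documents admit untrained readers, the only overall estimate pools everyone, and no prespecified estimate or subgroup level isolates reads made after training from the rest. The pooled figure is valid as the error rate in practice; it is the accuracy of trained readers only if every read followed training.

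The size cannot be derived from the documents. It is zero with no untrained or pre-training reads, and 0.8 to 1.5 points for one untrained reader at the cap under the assumed accuracy of 70% to 80%. The textual gap is certain. The consequence depends on who enrols and on when existing images were read. The widths above assume independent reads; clustering by reader would widen them.

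**What to change.** 1. **SAP sections 4.1 and 8.6.2.** Keep the all-reader estimate, labelled as the interpretation error rate in clinical practice. Add one prespecified supportive estimate of the five measures, with exact 95% intervals, restricted to reads dated after the reader completed VIZAMYL training. Describe it as accuracy after training and not as an effect of training, since there is no comparator.
2. **SAP section 8.6.3.** Add training status at the read (trained, not trained, unknown) as a by-variable, and add a level for none to training method and to time from training.
3. **SAP section 7.1.** State one rule: only training completed before the read date counts, and reads made before training go to none, not to the under-6-months level. If training dates are not linked to method for readers who had both, keep method at reader level.
4. **SAP section 9.** Record these additions.

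Training status, method and dates are already collected (Protocol Table 5), and eligibility and enrolment do not change. The cost is a few more table rows and a wider interval for the restricted set: 9.1 to 9.3 points at 185 reads, 9.9 at 160 and 10.6 at 140, against 8.8 at 200. A row for untrained reads would be very imprecise: 12 of 15 correct gives 51.9% to 95.7%.
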